8.2 INDEX PROCEDURE (DAY 0)

The following assessments will be collected on the day of index procedure.

- Procedural data
- Adverse event assessment
- Supra-aortic angiogram or TEE (if performed per standard practice)

8.3 POST-PROCEDURE

The following assessments will be collected within 72 hours post index procedure

- Adverse event assessment
- Laboratory tests (Complete Blood Count and Comprehensive Metabolic Panel)
- Vital signs
- 12-Lead ECG
- Transthoracic Echocardiogram (TTE).

8.4 DISCHARGE or 7 DAYS POST-PROCEDURE (whichever is first)

The following assessments will be collected on the day of discharge (or 7 days post index procedure if the patient is not discharged by the 7th day). If the patient is discharged within 72 hours of index procedure, the post-procedure assessment should not be repeated.

- Physical Exam and vital signs
- Concomitant medications
- Adverse event assessment
- NIH Stroke Scale (NIHSS)
- Laboratory Test (Complete Blood Count and Comprehensive Metabolic Panel)
- 12-Lead ECG
- NYHA Classification
- QOR-15 scale (Quality of recovery)

8.5 30 DAY VISIT

The following assessments will be collected at 30 days (+ or – 7 days) from index-procedure.

- Physical Exam and vital signs
- Concomitant medications
- Adverse event assessment
- NIH Stroke Scale (NIHSS) and Modified Rankin Scale (mRS)
- Laboratory Test (Complete Blood Count, Comprehensive Metabolic Panel, and NT-proBNP)
- 12-Lead ECG
- Transthoracic Echocardiogram (TTE)
- NYHA Classification
- 6-Minute Walk Test
- Kansas City Cardiomyopathy Questionnaire (KCCQ)
- SF-12 Questionnaire
- QOR-15 scale (Quality of recovery)
- PHQ-9 scale (Depression score)

8.6 1 YEAR VISIT

The following assessments will be collected at 1 year (+ or – 30 days) from index-procedure.

- Physical Exam and vital signs
- Concomitant medications
- Adverse event assessment
- NIH Stroke Scale (NIHSS) and Modified Rankin Scale (mRS) (only for patients who develop a stroke post-index procedure)
- Laboratory Test (Complete Blood Count, Comprehensive Metabolic Panel, and NT-proBNP)
- 12-Lead ECG
- Transthoracic Echocardiogram (TTE)
- NYHA Classification
- 6-Minute Walk Test
- Kansas City Cardiomyopathy Questionnaire (KCCQ)
- SF-12 Questionnaire
- QOR-15 scale (Quality of recovery)
- PHQ-9 scale (Depression score)

8.7 ANNUAL (2 to 10 YEAR) VISITS

The following assessments will be collected at 2 to 10 years (annually) (+ or – 45 days) from index-procedure.

- Physical Exam and vital signs
- Concomitant medications
- Adverse event assessment, including assessment of re-interventions or re-hospitalizations
- 12-Lead ECG (If available per standard of care)
- Transthoracic Echocardiogram (TTE)
- NYHA Classification
- Kansas City Cardiomyopathy Questionnaire (KCCQ)
- SF-12 Questionnaire
- PHQ-9 scale (Depression score)

8.8 EFFECTIVENESS ASSESSMENTS

The specific timing of procedures/evaluations and timing at each study visit are captured in **Section 1.3, Schedule of Activities (SoA)**.

- The majority of these procedures/evaluations will be completed during the study as part of regular standard of clinical care.
- This is except for specified functional and quality of life metrics which are supplemental and specified in section 1.3.

If an individual's medical chart or results of diagnostic tests performed as part of an individual's regular medical care are going to be used for screening or as a part of collection of trial data, Health Insurance Portability and Accountability Act (HIPAA) rules, other relevant federal or state laws, and local institutional requirements will be followed, as applicable. This includes corelab review of deidentified echocardiographic and CT data.

8.9 SAFETY AND OTHER ASSESSMENTS

These are as for the efficacy assessments, and specified in are captured in **Section 1.3, Schedule of Activities (SoA)**.

8.10 ADVERSE EVENTS AND SERIOUS ADVERSE EVENTS

8.10.1 Definition of Adverse Events and Reportable Adverse Events for the BELIEVERS trial

An adverse event (AE) is any untoward medical occurrence associated with the use of an intervention, whether or not considered intervention related. Given this study is comparing commercially approved devices, reportable AEs for the BELIEVERS trial will be **restricted to those AEs (both serious and non-serious) corresponding to the study's primary, secondary and safety endpoints derived directly from site reporting** (table 1); those primary, secondary, safety and exploratory endpoints derived from echocardiography or CT corelabs will be reported directly to the DCC by the respective corelabs.

Other reportable AEs complications that can occur include clinical or subclinical valve thrombosis, bioprosthetic valve failure, valve reintervention, valve or heart-failure related hospitalization. Additional details on events that will require reporting will be specified in the MOP and specific guidance in this regard will be provided by the CCC to the sites on site initiation and to the CEC.

8.10.2 Definition of Serious Adverse Events (SAE)

An adverse event (AE) or suspected adverse reaction is considered serious if, in the view of either the investigator or sponsor, it results in any of the following outcomes:

- Leads to death;
- Leads to a serious deterioration in the health of the study patient that:
 - Results in life-threatening illness or injury;
 - Results in a permanent impairment of a body structure or a body function;
 - Requires inpatient hospitalization or prolongation of existing hospitalization;
 - Results in medical or surgical intervention to prevent permanent impairment to body structure or a body function;
- Led to fetal distress, fetal death or congenital abnormality or birth defect;
- Significant medical event.

Important medical events that may not result in death, be life-threatening, or require hospitalization may be considered serious when, based upon appropriate medical judgment, they may jeopardize the patient and may require medical or surgical intervention to prevent one of the outcomes listed in this definition. Examples of such medical events include allergic bronchospasm requiring intensive treatment in an emergency room or at home, blood dyscrasias or convulsions that do not result in inpatient hospitalization, or the development of drug dependency or drug abuse.

8.10.3 Classification of an Adverse Event

8.10.3.1 Severity of Event

For adverse events (AEs) not included in the protocol-defined grading system (based on VARC-3), the following guidelines will be used to describe severity.

- **Mild** – Events require minimal or no treatment and do not interfere with the patient's daily activities.
- **Moderate** – Events result in a low level of inconvenience or concern with the therapeutic measures. Moderate events may cause some interference with functioning.
- **Severe** – Events interrupt a patient's usual daily activity and may require systemic drug

therapy or other treatment. Severe events are usually potentially life-threatening or incapacitating. Of note, the term “severe” does not necessarily equate to “serious”.

8.10.3.2 Relationship To Study Intervention

All adverse events (AEs) must have their relationship to study intervention assessed by the clinician who examines and evaluates the patient based on temporal relationship and his/her clinical judgment. The level of causality/relatedness will be graded using the categories below, in line with the Academic Research Consortium Steering group followed by the majority of transcatheter device trials (2):

- **Not related:**
 - Event is not a plausible consequence of use of the device;
 - Temporal relationship is not consistent with device use;
 - Event is attributable to another cause;
 - No evidence of device deficiency or use error.
- **Possible:**
 - Information to assess relationship is not available;
 - Evidence is weak but relationship cannot be excluded;
 - Alternative causes are also possible.
- **Probable:**
 - Relationship with use of device seems relevant;
 - Event cannot reasonably be explained by another cause.
- **Definite (causal):**
 - Event is associated with a known side effect or complication of device;
 - Temporal relationship to use of device;
 - Event follows a known response pattern to use of the device;
 - Other possible causes have been adequately excluded;
 - Event is related to error in use.

8.10.3.3 Expectedness of adverse events

Reportable Adverse Events for the BELIEVERS trial are described in section 8.10.1 above and reiterated below.

Both the site treating the patient and the clinical events committee (CEC) specified in the MOP will be responsible for determining whether an adverse event (AE) is expected or unexpected. An AE will be considered unexpected if the nature, severity, or frequency of the event is not consistent with the risk information previously described for the study intervention. The site and CEC-determined expectedness will both be documented.

For clarity, in this study, the following events **will be** required to be reported to the CCC/CEC:

- Death
- Disabling stroke
- Non-disabling stroke
- Valve reintervention
- Rehospitalization (valve or procedure related and including heart failure but excluding valve

reintervention)

- Rehospitalization (*valve-, procedure-, or HF-related*)
- CV rehospitalization
- Myocardial infarction
- Coronary obstruction
- Cardiovascular Injury including aortic root injury, aortic dissection, valvular or myocardial injury, ventricular perforation
- Need for surgery of the aorta
- Major bleeding (VARC-3)
- Major vascular complication (VARC-3)
- Access Site Infection
- Cardiac structural complication (major)
- Need for open heart surgery
- Arrhythmia including atrial fibrillation/ atrial flutter
- Device malpositioning (including embolization and migration)
- Endocarditis (valve-related)
- Acute Kidney Injury stage 3-4
- Clinically significant valve thrombosis
- Need for permanent pacemaker
- Valve-related mortality.

8.10.4 Time Period and Frequency For Event Assessment And Follow-Up

The occurrence of an adverse event (AE) or serious adverse event (SAE) may come to the attention of study personnel during study visits and interviews of a study patient presenting for medical care, or upon review by a study monitor.

AEs including local and systemic reactions not meeting the criteria for SAEs will be captured on the appropriate case report form (CRF). Information to be collected includes event description, time of onset, clinician's assessment of severity, relationship to study product (assessed only by those with the training and authority to make a diagnosis), and time of resolution/stabilization of the event. All reported AEs occurring while on study must be documented appropriately regardless of relationship. All AEs will be followed to adequate resolution.

Any medical condition that is present at the time that the patient is screened will be considered as baseline and not reported as an AE. However, if the study patient's condition deteriorates at any time during the study, it will be recorded as an AE.

8.10.5 Adverse Event Reporting

All relevant AEs and SAEs (as defined in VARC-3) will be captured from the time of randomization until the study patient's participation has ended (i.e., completion of study or withdrawal of consent), time period as specified above.

Adverse events must be followed until resolution, stabilization, or study completion. The AE and/or SAE should be reported to the sponsor, and CRF Forms completed **as soon as possible but no later than 10 working days of awareness**.

This study uses standard-of-care procedures and FDA-approved, commercially available devices. Therefore, IRB reporting will follow institutional and local IRB requirements for AEs/SAEs, and endpoint clinical events will additionally be captured and adjudicated by the CEC throughout follow-up as specified in the protocol

and MOP.

8.11 STUDY PROCEDURES/ASSESSMENTS

8.11.1 Neurologic Event Identification and Stroke Assessment Pathway

Any suspected new neurologic deficit occurring after randomization (including peri-procedural events) will trigger the following standardized pathway to support consistent diagnosis, disability classification, and CEC adjudication.

1. **Recognition and initial response**
 - If a new focal neurologic deficit, altered mental status, seizure, or visual loss is observed or reported, site staff will initiate the institution's **stroke alert** process and notify the treating team immediately.
 - A focused neurologic exam will be performed as soon as feasible.
2. **Neurologic assessment (NIHSS)**
 - **NIHSS** will be performed at the time stroke is suspected/identified, preferably by a neurologist or a trained/certified assessor.
 - NIHSS timing and score will be documented in the source record.
3. **Neuroimaging and diagnostic work-up**
 - Brain imaging (non-contrast CT and/or MRI) and additional vascular imaging (CTA/MRA) will be obtained per local standard of care and documented.
 - If symptoms resolve rapidly, evaluation should still occur to support classification as stroke vs TIA.
4. **Event classification (Stroke vs TIA vs non-neurologic event)**
 - Events will be classified clinically using protocol endpoint definitions and available imaging.
 - **TIA** is considered when symptoms resolve and there is no imaging evidence of acute infarction, per endpoint definitions.
5. **Disability assessment (mRS)**
 - For confirmed stroke, **mRS** will be assessed at approximately **90 days** post-stroke (acceptable window **30–90 days** if needed), preferably by a neurologist or trained/certified assessor.
 - A pre-stroke baseline mRS (most recent pre-event functional status) will be documented to support disability change assessment.
6. **CEC adjudication packet**

Sites will submit a standardized stroke packet to the CEC including:

 - admission/discharge summaries, neurology notes, procedure notes (if peri-procedural), NIHSS documentation, mRS assessment documentation, and neuroimaging reports (and images if required by the charter), plus relevant labs and ECG rhythm documentation.
7. **Clinical care**

This pathway does not supersede clinical care. All diagnostic and treatment decisions remain the responsibility of the treating clinicians.

9 STATISTICAL CONSIDERATIONS

9.1 STATISTICAL HYPOTHESES

The null hypothesis is that there is **no difference between TAVR and SAVR** in relation to the hierarchical primary composite endpoint. The alternative hypothesis is that **TAVR differs from SAVR**. The test for superiority is two-sided, such that SAVR or TAVR superiority could be demonstrated.

Primary Efficacy Endpoint: **A hierarchical composite** of: (1) death, (2) disabling stroke, (3) non-disabling

stroke, (4) valve reintervention, (5) rehospitalization, (6) unfavorable KCCQ (VARC-3).

Secondary Efficacy Endpoint(s): Specified in section 1.1.

9.2 SAMPLE SIZE DETERMINATION

The study sample size has been calculated to achieve 85% power for the hierarchical composite outcome under the expected event rates given in Table 2 below. The expected SAVR event rate of 25.4% is based on 3-year SAVR rates from the PARTNER low risk study(3). This is a conservative approach since most patients will have more than 3 years follow-up and all patient data collected within the 6-year funded study period will be included. Comparisons in the win ratio are based on the most severe event experienced by each patient: we provide the assumed distribution of the most severe component of the primary outcome in the Table which is based on data from PARTNER-3. The assumed TAVR rates are then calculated assuming a relative risk of 0.75 comparing SAVR to TAVR.

Why we chose 25% surgical advantage (RR = 0.75) as a *reasonable estimate*:

- **Evidence spectrum:** randomized data (NOTION-2)(4) suggests a **~70 % benefit for surgery**, but this remains an inconclusive study given a very small sample size (n=100) designed for non-inferiority, but confidence intervals were very wide and spanned 1.0; the large Medicare dataset also suggesting survival advantage with SAVR though retrospective and claims-based. In addition, several administrative or meta-analytic datasets that show anywhere from **neutral to a small TAVR advantage**. Our assumption (25% benefit) sits **midway between clear surgical advantage to a possible slight TAVR edge**, acknowledging residual uncertainty.
- **Clinical plausibility:** Surgery, in removing the native leaflets, eliminates the impact of high TAVR risk anatomy (excessive valve and raphe calcium) yet TAVR, with less invasiveness offers significant putative advantages, reflected in early follow up data from the TAVR vs SAVR trials in tricuspid aortic valve. A **25% composite difference** balances these competing effects.
- **Bottom line:** Published 1-year results range widely from strong surgical benefit to slight TAVR benefit depending on data source and methodology. All involve predominantly older, higher-risk patients. Thus, in the presence of enormous uncertainty, using RR = 0.75 represents a *conservative midpoint* that:
 - Reflects the full observed range,
 - Incorporates known anatomic/mechanical advantages of SAVR in BAV, and
 - Preserves statistical power without over-promising effect size.

Moreover, the use of a win ratio of 1.33 (corresponding to a RR of < 0.75) is consistent with recent uses of the win ratio in cardiovascular trials. Many cardiovascular trials in the last 2 years have used the win ratio and declared a significant benefit of intervention (summarized in a systematic review of trials by Gregson, Pocock and colleagues currently *in press* in the journal *Circulation*). Amongst these studies, in the majority the estimated win ratio was greater than 1.33 (corresponding to a RR of < 0.75)

Table 2: Assumed distribution of the primary outcome used for sample size calculations		
Outcome	Assumed SAVR rate	Assumed TAVR rate
Death	5.3%	7.1%
Disabling stroke	1.1%	1.5%
Non-disabling stroke	3.0%	4.0%
Valve re-intervention	1.7%	2.3%
Re-hospitalization	9.3%	12.5%
Unfavorable KCCQ*	5.0%	6.7%
None of the above	74.6%	65.9%

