9.4 STATISTICAL ANALYSES

9.4.1 General Approach

Under the stated assumptions, we used 10,000 simulated trials to determine that 1020 patients with complete 3-year data achieves 85.3% power for a two-sided Finkelstein-Schoenfeld at a 5% significance level. Simulations randomly generated time-to-event data for each clinical event using an exponential distribution, with the rates for each component tailored so that the distribution of the most severe outcome within each patient followed the distribution given in Table 2. KCCQ outcomes were randomly generated from a binomial distribution. To allow for a small number of crossovers, loss-to-follow up (estimated at around an eighth or 12.5% of patients, in line with PARTNER trials), we propose to recruit a total of **1,200 randomized patients, 600 in each arm**. This sample size yields >95% power for the analysis of the key secondary outcome (a hierarchical composite of death and time-averaged KCCQ score) if SAVR improves the average KCCQ score by 3 points under the assumption that the standard deviation of an individual KCCQ measurement is 20. **Our key secondary outcome** is similar to the primary endpoint of the PCORI-funded RECHARGE study, which will study a hierarchical composite of death and SF-12 quality of life assessment, using the win ratio(5). Such a magnitude of improvement in KCCQ is regarded as clinically meaningful and, in context, is similar to that seen in novel heart failure drugs that have impacted survival and quality of life(6).

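### Section 9.2 gives the planning win ratio as 1.33, but the Table 2 rates behind the 85% power imply about 1.41–1.42; the benchmark against published trials therefore uses a smaller effect than the one powered for

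*Protocol*

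**What the plan says.** Section 9.2 rests the sample size on Table 2: "The study sample size has been calculated to achieve 85% power for the hierarchical composite outcome under the expected event rates given in Table 2". The control side is described as follows: "The expected SAVR event rate of 25.4% is based on 3-year SAVR rates". For the other arm, "The assumed TAVR rates are then calculated assuming a relative risk of 0.75 comparing SAVR to TAVR". Table 2 then lists the worst outcome per patient in six tiers plus no event, adding up to 25.4% with any event on SAVR and 34.1% on TAVR.

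Section 9.4.1 reports the result of 10,000 simulated trials with exponential event times and a binary KCCQ tier, tuned to Table 2: "1020 patients with complete 3-year data achieves 85.3% power for a two-sided Finkelstein-Schoenfeld at a 5% significance level".

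Between the two, section 9.2 adds an argument from precedent: "the use of a win ratio of 1.33 (corresponding to a RR of < 0.75) is consistent with recent uses". It then says that in most recent cardiovascular trials declaring a benefit by win ratio the estimate exceeded 1.33, and attaches the same relative-risk correspondence a second time. No other win ratio is offered as the planning value.

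**The concern.** The win ratio 1.33 and the relative risk 0.75 are presented as the same effect. They would be the same only if events were rare. Here a quarter to a third of patients have an event, so the two scales separate.

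This matters because the primary result will be reported as a win ratio. The funder, the DSMB and later readers will set it beside the only planning win ratio in the protocol. The appeal to published trials also depends on this figure: if the design effect is really above 1.4, showing that most positive trials exceeded 1.33 does not show that they exceeded the effect this trial is powered for.

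**Working it through.** **Inputs.** Table 2 worst-outcome percentages, SAVR / TAVR: death 5.3 / 7.1, disabling stroke 1.1 / 1.5, non-disabling stroke 3.0 / 4.0, reintervention 1.7 / 2.3, rehospitalization 9.3 / 12.5, unfavorable KCCQ 5.0 / 6.7, none 74.6 / 65.9. From 9.4.1: 1,020 evaluable (510 per arm), two-sided 5% Finkelstein-Schoenfeld test, exponential event times. Assumptions added here: independent tiers and a common 3-year follow-up.

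**1. The plan's own power.** Rebuilding that simulation with 10,000 trials gives 84.8%, against the stated 85.3%. It reproduces. The average win ratio in those trials is 1.42. (With TAVR rates at exactly SAVR/0.75, without Table 2's rounding, simulated power is 82.9%.)

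**2. Win ratio from Table 2 alone.** Compare worst categories only and call pairs in the same category ties. SAVR wins when the TAVR patient is in tier k and the SAVR patient is in a better category; losses are the mirror image.

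| Tier | SAVR wins | SAVR loses |
|---|---|---|
| Death | 0.071 × 0.947 = 0.0672 | 0.053 × 0.929 = 0.0492 |
| Disabling stroke | 0.015 × 0.936 = 0.0140 | 0.011 × 0.914 = 0.0101 |
| Non-disabling stroke | 0.040 × 0.906 = 0.0362 | 0.030 × 0.874 = 0.0262 |
| Reintervention | 0.023 × 0.889 = 0.0204 | 0.017 × 0.851 = 0.0145 |
| Rehospitalization | 0.125 × 0.796 = 0.0995 | 0.093 × 0.726 = 0.0675 |
| Unfavorable KCCQ | 0.067 × 0.746 = 0.0500 | 0.050 × 0.659 = 0.0330 |
| Sum | 0.2874 | 0.2004 |

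Win ratio = 0.2874 / 0.2004 = 1.43.

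**3. Win ratio with event timing, as 9.4.1 models it.** For tiers 1–5, let a and b be the SAVR and TAVR event probabilities among patients with nothing worse, with A = −ln(1 − a) and B = −ln(1 − b). Among pairs still tied, SAVR wins [1 − (1 − a)(1 − b)] × B/(A + B) and loses the same with A on top. For death: a = 0.053, b = 0.071, 1 − 0.947 × 0.929 = 0.1202, split 0.0691 to 0.0511. Over all six tiers SAVR wins 29.6%, loses 20.9% and ties 49.5%. Win ratio = 0.2961 / 0.2090 = 1.417. With the relative risk at exactly 0.75 it is 1.405.

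**4. Why it is not 1/RR.** The ratio of the totals is 0.341 / 0.254 = 1.34. If the endpoint were one yes/no outcome, the win ratio would be the odds ratio, (0.341 × 0.746) / (0.254 × 0.659) = 1.52. The hierarchical, time-resolved comparison falls between the two.

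**5. What 1.33 corresponds to.** Scaling Table 2 proportionally until the time-resolved win ratio is 1.33 gives RR 0.785 with SAVR rates held fixed and 0.787 with TAVR rates held fixed.

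**6. Power at a true win ratio of 1.33.** Normal check: 85.3% power means a standardized effect of 1.96 + 1.05 = 3.01. Scaling on the log win ratio, 3.01 × ln 1.33 / ln 1.417 = 3.01 × 0.285 / 0.349 = 2.46, and Φ(2.46 − 1.96) = 69%. Simulation at 1,020 gives 68.1% (SAVR fixed) and 70.3% (TAVR fixed); a separate run gave 67% at the lower end. With all 1,200 evaluable, simulation gives from 73.9% to 76%; the normal check gives 2.46 × √(1200/1020) = 2.67, or 76%.

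**The case against.** The best defence is that 1.33 is not an input. The power is tied to Table 2, the simulation draws from Table 2, and the result reproduces. The figure sits in a supporting paragraph on precedent, and no test, sample size or analysis uses it. All of that stands, and it sets the weight of the point.

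Four stronger readings are tempting, and the documents do not support them.

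- A reader might infer that the protocol claims 85% power at a win ratio of 1.33. It never says so; it claims that power under Table 2.
- A reader might infer that the trial must observe 1.42 to succeed. That is the true effect giving about 85% power. With a simulated standard deviation of the log win ratio of 0.118, an observed value near exp(1.96 × 0.118) = 1.26 would reach two-sided p < 0.05 with 1,020 patients.
- A reader might say that the inequality in the parenthesis is reversed. Its direction, larger win ratio and smaller relative risk, is right; the fault is treating one as the inverse of the other. Where the phrase describes other trials, it cannot be checked, because their event and tie rates are not in the protocol.
- A reader might conclude that most published positive trials fall short of 1.42. The review relied on is not among the documents, so this is unknown.

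The objection that power at 1.33 is not one fixed number also stands. It depends on how the rates are scaled and on 3-year data. Section 9.2 expects most patients to be followed longer; at the same win ratio, more events would raise power, by an amount the protocol does not quantify.

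**Conclusion.** The point holds as an error in the effect-size justification, and it should be fixed. The planning win ratio consistent with relative risk 0.75 and Table 2 is about 1.41–1.42 under the protocol's event-time model, or 1.43 if pairs sharing a worst category are tied; none of these variants gives 1.33. At these rates 1.33 corresponds to a relative risk of about 0.785. The comparison with published trials is therefore made at a smaller effect than the one powered for, and whether its conclusion survives at 1.42 cannot be judged from the protocol. Power if the true win ratio were 1.33 is roughly 67–70% with 1,020 evaluable patients and 74–76% with 1,200. These figures assume independent tiers, proportional scaling of Table 2 and 3-year data. The stated 85.3%, Table 2 and the sample size are unaffected.

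**What to change.** In section 9.2:

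- Replace 1.33 with about 1.41–1.42 as the win ratio matching a relative risk of 0.75, preferably the mean from the sponsor's own simulations.
- Correct the correspondence: at the Table 2 rates, 1.33 goes with a relative risk of about 0.785. Remove the implied conversion for other trials unless it is worked out from their own event rates.
- Repeat the comparison with published win ratios against about 1.42, and report what it shows.
- Add one sensitivity line: power of roughly 67–70% at a true win ratio of 1.33 with 1,020 evaluable patients (about 74–76% with 1,200), for 3-year data and proportional scaling, and higher if longer follow-up adds events.

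The cost is a few sentences and a second look at the cited review. The precedent argument may come out weaker. The number of patients, the test and the analysis do not change.
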